7 INSTRUMENTS

The following outcome measures will be utilized to represent meaningful measurements of therapy success:

1. Apnea-hypopnea index (AHI) - is an index of sleep apnea severity that combines the frequency of apnea and hypopnea events. The severity of obstructive sleep apnea is determined by the measurement of apneas and hypopneas. An obstructive apnea is defined as a cessation (> 90% decrease) of airflow for at least 10 seconds with breathing effort; and a hypopnea is defined as an event with at least a 30% reduction in airflow lasting at least 10 seconds, and with $\geq 4\%$ oxygen desaturation. The frequency of apneas and hypopneas per hour of sleep is termed the apnea-hypopnea index (AHI). AHI values are typically categorized as 5–15/hr = mild; 15–30/hr = moderate; and $> 30/h$ = severe. AHI will be determined at baseline and at the 6-months follow-up visit.
2. Oxygen Desaturation Index (ODI) – ODI is defined as the number oxygen desaturation events, where there is a $\geq 4\%$ desaturation from pre-event baseline, that occur per hour of sleep. ODI generally correlates well with AHI [15], and it is reasonable to conclude that a 25% reduction in ODI represents a

Seite 34 von 54

Protocol 990211 RAMOSA

RFA for multi-level OSA

Protocol version 6.0 from 26th September 2014

clinically meaningful improvement. ODI will be determined at baseline and at the 6 months follow-up visit.

3. Epworth Sleepiness Scale (ESS) - The ESS is a validated, self-report instrument that rates a subject's tendency to fall asleep in eight common daily situations. The ESS Scale has been validated primarily in OSA. It is used to measure excessive daytime sleepiness, and is often utilized before and after the administration of treatment (e.g. CPAP) to document improvement of symptoms. The patient will complete this questionnaire at the Baseline, at Visit 3 (prior to the 1st RFA treatment), Visit 4 (prior to the 2nd RFA treatment), at Visit 5 (prior to the 3rd RFA treatment), at Visit 6 (6 weeks follow-up post 3rd RFA treatment), and at Visit 7 (6 months follow-up).

4. Functional Outcomes of Sleep Questionnaire (FOSQ) - The FOSQ is a quality-of-life questionnaire designed specifically to evaluate the impact of disorders of excessive sleepiness on activities of daily living. This is a self-report measure that assesses the effect of excessive sleepiness on activities of ordinary living, including activity level, vigilance, intimacy and sexual relationships, general productivity, and social outcomes. The patient will complete a FOSQ at the Baseline, at Visit 3 (prior to the 1st RFA treatment), Visit 4 (prior to the 2nd RFA treatment), at Visit 5 (prior to the 3rd RFA treatment), at Visit 6 (6-Weeks follow-up post 3rd RFA treatment), and at Visit 7 (6-months follow-up).

5. Pain will be measured on a 10-point Visual analog Scale (VAS_{PAIN}, 0 = "no pain" and 10 = "severe pain"). Measurements will be done on day 1, 3, and 7 post (each) RFA treatment.

6. Snoring will be measured on a 10-point Visual analog Scale (VAS_{SNORING}) and filled out by the bed partner. This scale will be used to assess by the patient and his/her bed partner snoring levels. The scale will range from 0 (no snoring noise) to 10 (extreme noise - bed partner leaves the room). Measurements will be done on day 1, 3, and 7 after the first RFA treatment, on the 2nd and 3rd RF treatments, prior to the treatment and on both follow-up visits.

7. Functional parameters such as speech and swallowing will be measured on a 10-point Visual analog Scale (VAS_{SPEECH} / VAS_{SWALLOWING}) ranging from zero (no problems/not affected) to 10 (severe problems/severely affected). Measurements will be done on day 1, 3, and 7 post each RFA treatment.

8 STATISTICAL ANALYSES

All analyses and graphs will be performed with common statistical packages. In general, summary statistics will consist of the following:

Continuous variables will be summarized by the number of observations (n), the mean, the standard deviation (SD), the standard error (SE), the median, the minimum, maximum and 95% confidence limits about the mean.

Categorical variables will be summarized by frequency and percentage in the corresponding categories and associated 95% confidence limits.

8.1 Primary Efficacy Endpoint

The primary endpoint of AHI and ODI obtained at the 6-month follow-up will be compared to the Baseline measurement. The subject is a responder if the reduction in AHI is $\geq 50\%$, and ODI reduction is $\geq 25\%$. The proportion of subjects meeting the responder criteria among all included subjects will be evaluated using a one-sided 95% confidence interval. In addition one sample test of the proportion of patients meeting the PG at 6month is significantly different than 50%. The study is designed to demonstrate success rate of 20% beyond the PG of 50%. Proportion with 95% CI will be given using normal approximation to the Binomial. P-Value will be derived based on the exact binomial distribution of the null hypothesis, that is assuming $p=0.5$.

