3 HYPOTHESES AND DATA ANALYSIS

3.1 Primary Efficacy Endpoints

The primary effectiveness of the study is to demonstrate a clinically significant reduction of OSAS from Baseline PSG sleep study to the 6-month follow-up PSG in adults (≥ 22 years) with obstructive sleep apnea (AHI 10-30) and BMI ≤ 32 .

Effectiveness of the CelonProSleep *plus* will be assessed by demonstrating adequate reduction in AHI and ODI as defined below:

A responder to the CelonProSleep *plus* RFA treatment is defined as a patient with an AHI reduction $\geq 50\%$ **and** a reduction of their ODI $\geq 25\%$ at the 6-month follow-up PSG, and their AHI at the 6-month follow-up is < 20 .

The aim of the study is to show that at least 50% of participants met the primary endpoint above. This will be tested with one sided 97.5% confidence interval with $\pm 20\%$ margin of error^{73, 74}.

In order to record and analyze data for determining the primary endpoints, patients will undergo a PSG sleep study to establish a mean baseline AHI and ODI. Patients will then be treated with a series of three treatments of upper airway radiofrequency ablation with the bipolar electrosurgical electrode CelonProSleep *plus* (Olympus Winter & Ibe, Germany) over 18 weeks. The patient will undergo a second PSG sleep study at the final follow-up examination 6-months later. Mean changes in AHI will be compared for each individual and among all patients. Surgical success is defined if at least 50% of participants experience at least 50% reduction in AHI and 25% reduction in ODI (Performance Goal, PG=50%).

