3.1.3 Hypotheses

Null Hypothesis. Multi-level radiofrequency ablation of the upper airway in adults (age ≥ 22 years) with obstructive sleep apnea (AHI 10-30; Lowest O₂ sat $\geq 80\%$) results in no improvement as defined by the composite endpoint, Section 3.1.

$$\begin{aligned} H_0: \text{TT RAMOSA} &\leq \text{PG} \\ H_A: \text{TT RAMOSA} &> \text{PG}, \end{aligned}$$

where TT_{RAMOSA} is the proportion of AHI and ODI responders to the multi-level radiofrequency treatment. For this objective, the PG is established at 50%.

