3.2 Sample Size Rationale

The sample size proposed for this study is 48 patients. This sample size is comparable to that used in performance and safety studies using radiofrequency ablation for the treatment of upper airways (soft palate and base of tongue, Table 1). In fact, considerable clinical data on the efficacy and safety RFA in OSAS is available from prior studies on this topic.

Recommended sample size is n=48. Sample size is calculated for o the proportion of participants who meet the successes criteria as defined by the performance goal (PG) (Section 3.1).

The following sample size considerations are based on the assumptions that PG=50% with 5% significance level and 80% power.

The sample size of n=43 +10% dropouts, i.e. n=48, is calculated by using the normal approximation for the z-score for testing inference about a single proportion p;

$$H_0: P_0 < 50\%$$

$$H_1: P_1 \geq 50\%$$

$$\text{and } P_1 - P_0 \geq 20\%$$

Below is the output of PASS12 NCSS program for sample size calculation:

Analysis of One Proportion Tests								
Numeric Results for testing $H_0: P = P_0$ versus $H_1: P > P_0$								
Test Statistic: Z Test using S (P0)								
Power	Proportion	Given H0 (P0)	Given H1 (P1)	Difference (P1 - P0)	Target Alpha	Actual Alpha	Beta	Reject H0 If Z \geq This
$\alpha=0.025$								
0.8029	187	0.5000	0.6000	0.1000	0.0250	0.0285	0.1971	1.9600
0.8112	82	0.5000	0.6500	0.1500	0.0250	0.0299	0.1888	1.9600
0.8081	43	0.5000	0.7000	0.2000	0.0250	0.0330	0.1919	1.9600
0.81	26	0.5000	0.7500	0.2500	0.0250	0.0378	0.1805	1.9600

Note that the one the actual exact Alpha of 0.033 will meet the two sided 5% significance.

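### Section 8.1 pairs a normal-approximation interval with an exact binomial p-value; at a common one-sided level they disagree on the 50% goal at one count at n=43 and at n=48

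*Combined protocol and SAP*

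**What the plan says.** Section 8.1 says the responder proportion "will be evaluated using a one-sided 95% confidence interval", then adds a one-sample test against 50% ("In addition one sample test of the proportion of patients meeting the PG at 6month is significantly different than 50" per cent). On method it states that "Proportion with 95% CI will be given using normal approximation to the Binomial" and that "P-Value will be derived based on the exact binomial distribution of the null hypothesis", taken at p = 0.5. It mentions no continuity correction and does not say whether the p-value is one- or two-sided.

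Section 3.1 gives a different level for the same aim: "This will be tested with one sided 97.5% confidence interval". Section 3.1.3 sets the goal ("For this objective, the PG is established at 50" per cent).

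Section 3.2 sizes the trial on "PG=50% with 5% significance level and 80% power". The software output below that uses a Z test with the null variance, a target alpha of 0.025 and rejection at Z of 1.96 or more. For 50% against 70% it gives n = 43, power 0.8081 and actual alpha 0.0330. Section 8.3 repeats the power as 80.8%. Sections 2.2 and 3.2 plan 43 evaluable patients out of 48.

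**The concern.** An interval and a test of the same proportion should lead to the same conclusion. That is guaranteed only when the interval is the inversion of the test. A normal-approximation bound does not invert an exact binomial test, and with about 43 patients the gap is wide enough to change the verdict at the boundary.

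Two things are at stake. The trial could report a lower limit above 50% next to a p-value that does not reject, with the choice between them made after the data are known. And the reported lower limit, which is the end that decides success, would be somewhat too high.

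**Working it through.** **Inputs.** Goal p0 = 0.50 (Section 3.1.3); alternative 0.70 (Sections 3.2 and 8.1); n = 43 evaluable and 48 enrolled (Sections 2.2 and 3.2); one-sided levels 0.05 (Section 8.1) and 0.025 (Section 3.1). Assumption: the normal approximation is the uncorrected Wald form.

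**The plan's own figure.** The Z statistic is (x/43 − 0.5)/√(0.25/43). At x = 27 it is 1.677 and at x = 28 it is 1.982, so the sizing rule is 28 or more of 43. Its exact alpha is P(X ≥ 28 | 0.5) = 0.0330 and its power is P(X ≥ 28 | 0.7) = 0.8081. Both match Section 3.2.

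**Formulas.** Normal lower bound: p̂ − z√(p̂(1 − p̂)/n). Exact p: P(X ≥ x | n, 0.5). Exact bound: the Clopper-Pearson lower limit.

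**Boundary at n = 43.**
- Level 0.025, x = 28: p̂ = 0.6512, standard error 0.0727. Normal bound 0.6512 − 1.96 × 0.0727 = 0.509, above 0.50. Exact p = 0.0330, above 0.025. Exact bound 0.491.
- Level 0.05, x = 27: p̂ = 0.6279, standard error 0.0737. Normal bound 0.6279 − 1.645 × 0.0737 = 0.507, above 0.50. Exact p = 0.0631, above 0.05. Exact bound 0.491.

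The chance of landing on 28/43 is 10.0% at a true 70% and 12.7% at 65%. For 27/43 it is 7.5% and 11.9%.

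**Smallest count declared a success, by n.**

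| n | 0.025: normal / exact | 0.05: normal / exact |
|---|---|---|
| 42 | 28 / 28 | 27 / 27 |
| 43 | 28 / 29 | 27 / 28 |
| 44 | 29 / 29 | 28 / 28 |
| 45 | 29 / 30 | 28 / 29 |
| 46 | 30 / 31 | 29 / 30 |
| 47 | 30 / 31 | 29 / 30 |
| 48 | 31 / 32 | 30 / 31 |

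At n = 48, 31/48 gives a normal 97.5% bound of 0.5105 with p = 0.0297, and 30/48 gives a normal 95% bound of 0.5101 with p = 0.0557.

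**Non-coverage of the lower bound at n = 43, nominal 2.5%, by enumeration.**

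| True rate | Normal | Clopper-Pearson |
|---|---|---|
| 50% | 3.3% | 1.6% |
| 55% | 3.5% | 1.6% |
| 60% | 3.5% | 1.6% |
| 65% | 3.4% | 1.5% |
| 70% | 3.1% | 1.2% |
| 75% | 6.1% | 0.9% |
| 80% | 5.1% | 1.8% |

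**What each rule implies at n = 43.**

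| One-sided level | Rule | Count | Exact alpha | Power at 70% |
|---|---|---|---|---|
| 0.025 | normal interval | 28 | 0.033 | 80.8% |
| 0.025 | exact test | 29 | 0.016 | 70.8% |
| 0.05 | normal interval | 27 | 0.063 | 88.3% |
| 0.05 | exact test | 28 | 0.033 | 80.8% |

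**The case against.** **The interval may already lead.** Section 3.1 tests by interval, Section 8.1 names the interval first and introduces the test as an addition, and Section 3.2 sizes on a normal-theory Z test. That ordering favours the interval. It stops short of a rule for the case where the two disagree. If the interval does govern, its actual alpha is 0.033 or 0.063, against 0.025 or 0.05.

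**The interval may only be descriptive.** Section 8 promises 95% limits for every categorical variable, and a normal interval printed beside an exact p-value is common. But Sections 3.1 and 8.1 use the interval to test and evaluate the goal, so this defence does not carry.

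**The conflict depends on how levels are paired.** A reader might infer that the two methods clash whatever levels are chosen. The documents do not support that. A 97.5% normal interval (Section 3.1) paired with an exact test at one-sided 0.05 (one reading of the 5% in Section 3.2) needs 28/43 both ways. Conversely, if the p-value is two-sided at 0.05, its pairing with the one-sided 95% interval widens the conflict to both 27/43 and 28/43 (two-sided p 0.126 and 0.066).

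**It is narrow.** The gap is one count at a common level and vanishes at n = 42 and n = 44. It is nevertheless present at 43 and at every n from 45 to 48.

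**The reading of the method.** A score interval gives the same cut-offs as Wald at n = 43 and n = 48, so the conflict stays. A continuity correction would remove it at n = 43, but none is specified.

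**Conclusion.** Section 8.1 is wrong as written: the interval it prescribes does not match the test it prescribes. With both at the same one-sided level, one count at n = 43 and one at n = 48 gives opposite verdicts, and no explicit rule resolves them. At a true 70% the chance of that count at n = 43 is 10.0% (level 0.025) or 7.5% (level 0.05).

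The under-coverage is modest where the decision is made: 3.1% to 3.5% against 2.5% between the goal and the design alternative. The larger misses, 6.1% and 5.1%, occur at 75% and 80%. It should not be read as a law for every normal interval: the two-sided 95% version covers about 95.25% at a true 70% with n = 43.

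Nor should a reader infer that the 80.8% power was miscalculated. It is right for the 28/43 rule. It is not the power of the exact test at one-sided 0.025. The Section 3.2 remark that an exact alpha of 0.033 satisfies two-sided 5% does not hold, since 2 × 0.033 = 0.066.

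These results rest on the uncorrected normal interval and on interval and test sharing a level.

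**What to change.** In Section 8.1, replace the normal-approximation interval with the exact (Clopper-Pearson) lower bound at the same one-sided level as the exact test. That bound inverts the test, so the two agree at every count and every n. Name that one level in Sections 3.1, 3.2 and 8.1, state that the p-value is one-sided, and restate the decision count and power in Sections 3.2 and 8.3:

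- One-sided 0.025: success at 29/43 or more, exact alpha 0.016, power 70.8% at a true 70%.
- One-sided 0.05: success at 28/43 or more, exact alpha 0.033, power 80.8%.

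**Cost.** The edit is short, but it has consequences. The reported lower limit falls by about 2 points (30/43 at 97.5%: 53.9% instead of 56.0%). The exact bound is somewhat conservative, with 0.9% to 1.8% non-coverage against 2.5% over the rates checked. If 0.025 is kept, the power on record is 10 points lower (80.8 − 70.8), and the sponsor must accept that or revisit the sample size. Using a normal-theory p-value instead would also align the pair and keep 28/43, but at an actual alpha of 0.033 against 0.025.

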8.2 Additional Analysis

Demographic, medical history and operative characteristics will be summarized for the study cohort, by clinical site, and by groupings of all sites. At a minimum, this will include age, gender, race, weight, and BMI.

Supporting analyses will be conducted to provide additional information on the safety and efficacy of multi-level radiofrequency treatment. Descriptive statistics will be utilized to summarize all adverse events. Regression models evaluating the change of continuous outcomes of AHI and ODI as well as logistic regression for the categorical outcome of response to treatment as defined in the primary objective will be used. A description of the relationship between BMI change and effectiveness outcomes will be performed by a cross-tabulation of BMI change versus responder and non-responder groups.

Data collected on all enrolled study subjects will be analyzed on an intend-to-treat and as-treated basis. Disease information and demographic variables, such as age, ethnic group, and sex, will be summarized by means of summary statistics. A normality distribution test (Kolmogorov-Smirnov) will be performed for all variables. Simple descriptive statistics such as frequency, mean, standard deviation, minimum, and maximum will be calculated for all outcome variables. If these variables are not normally distributed, other descriptive measurements such as median and the interquartile range will be calculated. For comparison between pre- and post-treatment variables, McNemar's-will be used with categorical variables. For continuous variables, a paired t-Test (normal distribution) or a Wilcoxon signed rank Test (not normal distribution) will be used to compare data at visit 2 (Baseline) and at visit 6 (six weeks after final RFA treatment). In addition, for long longitudinal analysis a One-Way ANOVA with Repeated Measures (or mixed models) will be used to model the outcome and cofactors over the multiple time-points. Significant interactions will be followed up using post-hoc analysis with Holms' adjusted P-values.

Site homogeneity will be evaluating by testing the interaction term in the analysis of covariance (ANCOVA) at a significance level of 0.15.

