3.3 Secondary Efficacy Endpoints

To determine whether multi-level radiofrequency ablation of the upper airway in adults with OSAS with the CelonProSleep *plus* bipolar electrode improves daytime sleepiness, snoring, percentage sleep

time at $\text{SaO}_2 < 90\%$, and sleep-related quality of life without a significant increase in pain, speech or swallowing dysfunction.

The following tools will be applied in order to determine the secondary aims: (1) Epworth Sleepiness Scale (ESS); (2) Functional Outcomes of Sleep Questionnaire (FOSQ), (3) SaO_2 , and (4) 100 mm VAS scale concerning snoring. ESS, FOSQ, and $\text{VAS}_{\text{snoring}}$ will be assessed at Baseline, 6 weeks after completion of each upper airway RF ablation treatments, and 6 months post-treatment. The percentage sleep time with $\text{SaO}_2 < 90\%$ will be determined at the final 6-month PSG.

Secondary endpoint statistical analysis includes descriptive statistics of percentages, Means and SD; In cases in which inference will be added to the value, it will be then corrected with Holm's adjustment for testing multiplicity.

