3.4 Secondary Endpoints

Secondary endpoints will be examined to provide additional support and details of the primary endpoint findings concerning the RFA treatment. The secondary endpoints assess important patient-based clinical outcomes to compliment the biophysiological primary outcomes. It will be evaluated using mean change at 6-months follow-up from baseline. As supporting evidence, this will be tested with one-sided confidence interval with no corrections for multiple testing.

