3.4.4.2 Objective and Hypotheses

The SaO₂ secondary endpoint in this study will be determined by the SaO₂ percentage time below 90% during the 6-month PSG sleep study compared with the PSG sleep study at Baseline. The objective is to demonstrate a decrease in SaO₂ percentage time at 6-months.

$$H_0: \mu_{SaO_2\%time} \leq 0$$

$$H_A: \mu_{SaO_2\%time} > 0,$$

where $\mu_{SaO_2\%time}$ is the mean change in Percentage time with SaO₂ below 90% from Baseline to the 6-month follow-up. This hypothesis will be tested using one-sided 95% confidence interval around the mean SaO₂.

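### Minor: the 6-week test choice rests on a normality check that never names within-patient change, and percent sleep time below 90% saturation has only a mean-based interval

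*Combined protocol and SAP*

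**What the plan says.** Section 8.2 sets a general rule: "A normality distribution test (Kolmogorov-Smirnov) will be performed for all variables". For continuous pre/post comparisons, "a paired t-Test (normal distribution) or a Wilcoxon signed rank Test (not normal distribution) will be used", and the rule is limited in the same sentence: "to compare data at visit 2 (Baseline) and at visit 6 (six weeks after final RFA treatment". The section does not say which quantity must be normal for the t-test. For longitudinal data it offers "One-Way ANOVA with Repeated Measures (or mixed models", leaving the choice open.

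Section 3.4.4.2 deals with percent sleep time at SaO2 below 90%. The parameter is the mean change "from Baseline to the 6-month follow-up", and the method is "This hypothesis will be tested using one-sided 95% confidence interval around the mean". No rank test, transformation or fallback is named. Section 3.3 says that this measure "will be determined at the final 6-month PSG". The stated objective is a decrease, but the alternative hypothesis is a mean change above zero.

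Section 3.4 sets the level for secondary endpoints: "this will be tested with one-sided confidence interval with no corrections for multiple testing". Sections 3.4.1.2, 3.4.2.2 and 3.4.3.2 fix the same kind of mean-change interval for FOSQ, ESS and snoring VAS at 6 months.

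**The concern.** A paired t-test assumes something about the within-patient differences. The marginal shape of baseline or follow-up values does not settle that: skewed marginals can have normal differences, and normal marginals can have heavy-tailed ones. A check on all variables, with the differences unnamed, can therefore choose the test on the wrong quantity. It also leaves the choice to be settled after the data are seen.

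Percent time below 90% cannot fall below zero. The entry rules (lowest saturation at least 80%, exclusion of room-air SpO2 below 95%) push it towards zero, so a right-skewed distribution is plausible. A few patients with long desaturation could then dominate the mean and its standard error, and a real reduction could be missed. Section 8.2 offers no fallback, because its t-or-Wilcoxon rule stops at visit 6 while the follow-up PSG belongs to visit 7.

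A repeated-measures ANOVA in its usual form also drops any patient with one missed visit.

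**Working it through.** **The plan's own figure.** Section 3.2 gives the only power figure, for the primary proportion: n = 43, P0 = 0.50, P1 = 0.70, reject if Z is at least 1.96. With 28 responders, Z = (28/43 − 0.5)/√(0.25/43) = 0.1512/0.0762 = 1.98; with 27 it is 1.68. So the rule is 28 or more of 43, with exact alpha 0.0330 and power 0.8081. Both match the plan. No power is stated for any secondary or pre/post test.

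**What the normality check reaches.** Appendix I places PSG, and so AHI, ODI and percent time, at visits 2 and 7 only. ESS, FOSQ and snoring VAS are collected at visits 2 and 6. The check therefore governs those three at 6 weeks, with routine measures such as weight and blood pressure, and no 6-month test.

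**How the check behaves (n = 43, simulated).**
- Plain Kolmogorov-Smirnov at nominal 5%, with mean and SD estimated, rejected truly normal samples in 0.03% of runs.
- With log-normal raw values (log-SD 0.5) it flagged non-normality in 14% to 17% of runs, against 84% to 87% with Lilliefors critical values.
- Skewed raw values, normal differences: checks on raw values and on differences disagreed in 95% of runs, but power was 78.7% (raw) against 80.2% (differences).
- Normal raw values, heavy-tailed differences (t, 2 df): they disagreed in 65% of runs, with power 64.6% against 85.0%.

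The last two items used Lilliefors critical values. The cost runs from about 1.5 to about 20 points, depending on shape.

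**Percent time below 90%.** The documents give no median, SD or shape, so all of these are assumptions: log-normal, median 2%, the same 30% reduction in every patient, n = 43, one-sided 5%.

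| Between-patient log-SD | Per-night log-SD | Mean interval | Wilcoxon | Gap (points) |
|---|---|---|---|---|
| 0.5 | 0.4 | 96% | 98% | 2 |
| 0.5 | 0.6 | 73% | 81% | 8 |
| 1.0 | 0.4 | 85.4% | 97.3% | 11.9 |
| 1.0 | 0.6 | 57.6% | 77.9% | 20.3 |
| 1.3 | 0.4 | 76.6% | 95.9% | 19.3 |
| 1.3 | 0.6 | 48.6% | 74.5% | 25.9 |

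In the second row the overall log-SD is √(0.5² + 0.6²) = 0.78, so it is no longer mild skew. Repeat runs gave about 1 to 3 points for mild skew, about 12 to 29 for log-SD 1.0 to 1.3, and 12 to 22 with many zeros added. With no true change, the mean interval rejected in 4.4% to 5.0% of runs and Wilcoxon in 4.6% to 5.7%.

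**A different effect pattern.** Suppose only the third of patients with the highest percent time benefit (halved) and the rest do not change. Over the four settings with log-SD 1.0 to 1.3, the mean interval had 63% to 90% power and Wilcoxon 59% to 83%, a reversal of up to about 8 points. The size depends on how that third is defined. A repeat run gave 8 to 10 points when it was set by the patient's usual level, and 10 to 15 when it was set by the observed baseline night.

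**Repeated measures.** Appendix I schedules ESS and FOSQ at five visits (2, 4, 5, 6, 7). If 5% are missing independently at each (an assumption), complete cases are 0.95⁵ = 77%, or 0.77 × 43 ≈ 33 patients. Section 7 adds visit 3, which gives 0.95⁶ = 74%.

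**The case against.** A reader might infer that Section 8.2 tests raw values instead of changes, and that the declared endpoints inherit this error. The text does not support that. All variables is silent on differences, so the raw-value reading is natural but not stated. The rule also stops at visit 6, so it never reaches AHI, ODI, percent time or the 6-month FOSQ, ESS and snoring VAS tests. For the same reason, the truncation of baseline AHI to 10-30 is beside the point. Section 1.2 mentions home sleep studies at follow-up, but compares them with screening, not visit 2.

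A reader might also infer that the mean interval for percent time is invalid or simply inferior. It is neither. It concerns a paired change, it keeps its error rate, and it matches a hypothesis written about a mean. Wilcoxon's advantage depends on skew and on a roughly proportional effect, and it reverses if benefit sits in the worst patients. Moving to Wilcoxon also changes the estimand.

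Finally, the mixed model is already named, and it would recover nobody if run on the Full Analysis Set, which Section 8.4 limits to patients who completed all eight visits. The 5% missingness is assumed.

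All of this stands. It limits the scope and size of the point but leaves three gaps: the checked quantity is undefined, percent time has a single method with no sensitivity analysis, and the longitudinal method is left open.

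**Conclusion.** The point holds in a limited form, and its severity is minor. The check in Section 8.2 is weak and does not name the quantity that matters, with consequences only for supplementary 6-week comparisons. The percent-time test in Section 3.4.4.2 is valid but can lose power: about 1 to 3 points with mild skew and about 12 to 29 with log-SD 1.0 to 1.3 under a proportional reduction. It can gain about 8 points or more if benefit is confined to those with the longest desaturation. Every one of these figures rests on assumed shapes, since the documents give none.

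The direction of the hypothesis in Section 3.4.4.2 needs no assumption. As written, the alternative is an increase in percent time while the objective is a decrease. Section 3.4.3.2 handles the same situation correctly for snoring, with a change below zero.

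These are supportive analyses. The primary endpoint, its alpha and the sample size are unaffected.

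**What to change.** 1. **Section 8.2, pre/post tests.** Delete the normality check as a rule for choosing tests, or state that it applies to within-patient changes. Name one test per endpoint: for example, a paired t interval on the change for FOSQ, ESS and snoring VAS.
2. **Section 3.4.4.2.** Pre-specify the Wilcoxon signed-rank test at 6 months with a Hodges-Lehmann estimate and one-sided limit. Keep the mean change as a reported summary, so that an effect concentrated in the worst patients remains visible. Reword the hypothesis as a median-type shift and make its alternative a decrease.
3. **Section 8.2, longitudinal data.** Drop repeated-measures ANOVA and keep only the mixed model, fitted to all treated patients rather than to the Full Analysis Set.

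The cost is SAP wording; both tests and the mixed model are already named, and no new data are needed. The real price is that the percent-time estimand becomes a median-type shift instead of a mean. If the sponsor wants to keep the mean as the estimand, the lesser change is to correct the direction and add the rank-based analysis as a pre-specified sensitivity analysis.
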